#### **8.1.2.10. Maastricht Ankylosing Spondylitis Enthesitis Score**

The MASES is an index used to measure the severity of enthesitis (Heuft-Dorenbosch et al. 2003). The MASES assesses 13 sites for enthesitis using a score of “0” for no activity or “1” for activity. Sites assessed include costochondral 1 (right/left), costochondral 7 (right/left), spinal iliaca anterior superior (right/left), crista iliaca (right/left), spina iliaca posterior (right/left), processus spinosus L5, and Achilles tendon proximal insertion (right/left). The MASES is the sum of all site scores (range 0 to 13); higher scores indicate more severe enthesitis.

The MASES must be assessed by a rheumatologist or health care provider who meets the qualifications for study assessments.

#### **8.1.2.11. Spondyloarthritis Research Consortium of Canada–Enthesitis Score**

The SPARCC enthesitis is an index used to measure the severity of enthesitis (Maksymowych et al. 2009). The SPARCC assesses 16 sites for enthesitis using a score of “0” for no activity or “1” for activity. Sites assessed include Medial epicondyle (left/right [L/R]), Lateral epicondyle (L/R), Supraspinatus insertion into greater tuberosity of humerus (L/R), Greater trochanter (L/R), Quadriceps insertion into superior border of patella (L/R), Patellar ligament insertion into inferior pole of patella or tibial tubercle (L/R), Achilles tendon insertion into calcaneum (L/R), and Plantar fascia insertion into calcaneum (L/R). The SPARCC is the sum of all site scores (range 0 to 16). Higher scores indicate more severe enthesitis.

The SPARCC must be assessed by a rheumatologist or health care provider who meets the qualifications for study assessments.

#### **8.1.2.12. Peripheral Arthritis**

##### **8.1.2.12.1. Tender Joint Count**

The number of tender and painful joints will be determined by examination of 46 joints (23 joints on each side of the patient’s body). The 46 joints to be assessed and classified as tender or not tender are detailed in site training materials. Any joints that require intra-articular injections during the study (according to Section 6.8) are to be excluded from evaluation from the time of the injection to the conclusion of the study.

Joint assessments must be assessed by a rheumatologist or health care provider who meets the qualifications for study assessments. To minimize interobserver variation, particularly during the Blinded Treatment Dosing Period (Period 2), it is recommended that the same assessor performs the TJC for a given patient. Missing, replaced, ankylosed, or arthrodesed joints will be

identified by the investigator at the screening visit (Visit 1) and will be excluded from evaluation during the study.

The TJC data will be collected electronically.

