During Period 2, alteration of cDMARD dose or route, and/or introduction of a new cDMARD are not permitted, unless required for safety reasons. Conventional DMARDs can only be used as single agents and not in combination with other cDMARDs. If, at any time, the investigator believes that side effects or laboratory abnormalities may be attributable to the cDMARD, the cDMARD dose is to be lowered or the medication stopped.

Extended Treatment and Post-Treatment Follow-Up Periods (Periods 3 and 4):

During Periods 3 and 4, adjustment of allowed cDMARDs (for example, dose change, introduction, withdrawal of cDMARDs, or replacement of a current cDMARD with the introduction of a new cDMARD) is allowed after all assessments at Week 16 are completed. Not more than 1 adjustment of cDMARDs at 1 time within 12 weeks is recommended. Conventional DMARDs can only be used as single agents and not in combination with other cDMARDs. Any changes must be recorded in the eCRF.

For all study periods, the maximum allowed doses are 25 mg/week MTX, 400 mg/day hydroxychloroquine and 3 g/day sulfasalazine. Local standards of care are to be followed for concomitant administration of folic or folinic acid if MTX is taken, and for administration of other cDMARDs.

**Corticosteroids:**Blinded Treatment Dosing Period (Period 2):

*Oral corticosteroids:* If on oral corticosteroids, the dose must not exceed 10 mg/day of prednisone or its equivalent and must be stable for at least 4 weeks prior to baseline

randomization. During Period 2, treatment alterations in oral corticosteroid dose are strongly discouraged.

*Parenteral corticosteroids (IV, intramuscular, intra-articular):* Treatment with any parenteral corticosteroids is not permitted within 6 weeks prior to baseline or during Period 2.

*Inhaled and topical steroids:* Regular use of inhaled or topical steroids will be permitted during any study period.

Extended Treatment and Post-Treatment Follow-Up Periods (Periods 3 and 4):

*Oral corticosteroids:* As of Week 16, adjustments of oral corticosteroids are allowed, however the maximum dose is not to exceed 10 mg/day of prednisone or its equivalent at any time during these periods.

*Parenteral corticosteroids (IV, intramuscular, intra-articular):* As of Week 16, intra-articular injection of corticosteroid may be allowed, as needed. The joint injected must be designated along with the medication in the eCRF and must be recorded as unevaluable on the TJC/SJC assessment.

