		SPARCC enthesitis score = 0	SPARCC enthesitis score = 0 refers to complete resolution in enthesitis. Analysis of SPARCC enthesitis score = 0 only applies to patients with baseline enthesitis (SPARCC enthesitis >0).	Missing if observed value is missing
Tender Joint Count (TJC)	The number of tender and painful joints will be determined by examination	TJC total score	Adjusted sum of the pain/tenderness for all 46 joints:	If more than half of the joint scores are non-evaluable, the total score will be missing.

Measure	Description	Variable	Derivation / Comment	Imputation Approach if with Missing Components
	of 46 joints (23 joints on each side of the patient's body). The 46 joints are assessed and classified as tender or not tender		$\left(\frac{\text{sum of all joints checked to be painful/tender}}{\text{number of evaluable joints}} \right) \times 46$ 
See Appendix 4 for details.
	

Measure	Description	Variable	Derivation / Comment	Imputation Approach if with Missing Components
		TJC change from baseline	Calculated as: observed TJC – baseline TJC only applies to patients whose baseline TJC >0.	Missing if baseline or observed value is missing
		Proportion of patients with TJC = 0 when baseline TJC >0	TJC >0 refers to incidence of TJC. Analysis of TJC = 0 only applies to patients whose baseline TJC >0.	Missing if observed value is missing
Swollen Joint Count (SJC)	The number of swollen joints will be determined by examination of 44 joints (22 joints on each side of the patient’s body). The 44 joints are assessed and classified as swollen or not swollen.	SJC total score	Adjusted sum of the pain/tenderness for all 44 joints. $\left(\frac{\text{sum of all joints checked to be swollen}}{\text{number of evaluable joints}} \right) \times 44$ See Appendix 4 for details.	If more than half of the joint scores are nonevaluable, the total score will be missing.
		SJC change from baseline	Calculated as: observed SJC – baseline SJC Only applies to patients whose baseline SJC >0.	Missing if baseline or observed value is missing
		Proportion of patients with SJC = 0 when baseline SJC >0	SJC >0 refers to incidence of SJC. Analysis of SJC = 0 only applies to patients whose baseline SJC >0.	Missing if observed value is missing

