	MASES score = 0 (similarly SPARCC = 0)	Logistic regression analysis with NRI; Fisher's exact test with NRI	ITT Population with Baseline MASES >0 (or SPARCC >0)	IXE80Q2W & IXE80Q4W vs. placebo at Week 16 and all other postbaseline visits in Period 2	Other secondary efficacy analyses (Section 6.10.4).
		Descriptive statistics of MASES = 0 (or SPARCC=0)	Extended Treatment Period Population with Baseline MASES >0 (or SPARCC >0)	No treatment group comparisons during Period 3	Other secondary efficacy analyses (Section 6.10.4).
Peripheral Arthritis	TJC and SJC change from baseline	MMRM	ITT Population with baseline TJC >0 (or SJC >0)	IXE80Q2W & IXE80Q4W vs. placebo at Week 16 and all other postbaseline visits in Period 2	Other secondary efficacy analyses (Section 6.10.4).
		ANCOVA with mBOCF	ITT Population with baseline TJC >0 (or SJC >0)	IXE80Q2W & IXE80Q4W vs. placebo at Week 16 and all other postbaseline visits in Period 2	Other secondary efficacy analyses (Section 6.10.4).
		Descriptive statistics of change from baseline	Extended Treatment Period Population with baseline TJC >0 (or SJC >0)	No treatment group comparisons during Period 3	Other secondary efficacy analyses (Section 6.10.4).
	TJC = 0 (similarly, SJC = 0)	Logistic regression analysis with NRI; Fisher's exact test with NRI	ITT Population with Baseline TJC >0 (or SJC >0)	IXE80Q2W & IXE80Q4W vs. placebo at Week 16 and all other postbaseline visits in Period 2	Other secondary efficacy analyses (Section 6.10.4).

Measure	Variable	Analysis Method (Sections 6.1, 6.3)	Population (Section 6.1.5)	Comparison/Time Point	Analysis Type
		Descriptive statistics of TJC = 0 (or SJC =0)	Extended Treatment Period Population with Baseline TJC >0 (or SJC >0)	No treatment group comparisons during Period 3	Other secondary efficacy analyses (Section 6.10.4).
Anterior uveitis	Crude and exposure-adjusted incidence rates for patients with anterior uveitis	Fisher’s exact test and Poisson regression	ITT Population	IXE80Q2W & IXE80Q4W vs. placebo during Period 2	Other secondary efficacy analyses (Section 6.10.4).
		Descriptive statistics	Extended Treatment Period Population	No treatment group comparisons during Period 3	Other secondary efficacy analyses (Section 6.10.4).
		Descriptive statistics	ITT Population Who are Initially Randomized to Ixekizumab	No treatment group comparisons during Combined Periods 2 and 3	Other secondary efficacy analyses (Section 6.10.4).

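### From Week 16, a steroid-injected joint stays in the baseline joint count but leaves every later one, which shifts the descriptive Period 3 TJC/SJC summaries toward improvement

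*Protocol*

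**What the plan says.** Protocol Section 6.8 bars these injections in the placebo-controlled period: "Treatment with any parenteral corticosteroids is not permitted within 6 weeks prior to baseline or during Period 2". It then relaxes the rule: "As of Week 16, intra-articular injection of corticosteroid may be allowed, as needed". The injected joint is named in the eCRF and "must be recorded as unevaluable on the TJC/SJC assessment". Section 8.1.2.12.1 (TJC) states the exclusion, "Any joints that require intra-articular injections during the study (according to Section 6.8) are to be excluded from evaluation", and Section 8.1.2.12.2 (SJC) repeats it. Both sections fix how long this lasts: such joints "are to be excluded from evaluation from the time of the injection to the conclusion of the study".

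SAP Table RHBV.6.4 takes the "sum of all joints checked to be painful/tender", divides by the number of evaluable joints and multiplies by 46. SJC is scored the same way with 44. The total is missing only when more than half the joints are non-evaluable. Both entries refer to Appendix 4 for detail, and that appendix is redacted in the public SAP.

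The responder variables are restricted by baseline: "Analysis of TJC = 0 only applies to patients whose baseline TJC >0", and likewise for SJC. For Period 3, SAP Table RHBV.6.5 lists change from baseline and the proportion with a count of zero, both descriptive and without treatment comparison. SAP Section 6.1.2 keeps the efficacy baseline at the last value before the first Period 2 injection of study treatment, usually Week 0.

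**The concern.** Joints that are missing, replaced, ankylosed or arthrodesed at screening drop out of both baseline and follow-up, so excluding them is even-handed. An injected joint drops out of follow-up only. If it was active at baseline, its removal lowers the later count whether or not it improved, and the error always runs toward improvement.

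Maintenance of effect through Week 52 is a stated secondary objective covering all the Period 2 endpoints, peripheral arthritis by TJC and SJC among them. At stake is whether a Period 3 count of zero can be read as absence of active joints when the joint in question received added local treatment and was then no longer examined. The groups may also be affected unequally, because the protocol synopsis lets investigators modify concomitant medication to control symptoms during the adalimumab washout.

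**Working it through.** The plan states no figure for this point, so the check applies its own scoring rule.

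**Inputs**
- Joints assessed: 46 for TJC, 44 for SJC (Protocol 8.1.2.12.1 and 8.1.2.12.2).
- Score = active joints / evaluable joints × 46 or 44 (SAP Table RHBV.6.4).
- Missing if more than 23 of 46, or more than 22 of 44, joints are non-evaluable (same table).
- Nonresponder imputation covers unmet criteria, missing response data and stopping study treatment (SAP 6.3.1). An injection is not listed.

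**One active joint, later injected**
- TJC: baseline 1/46 × 46 = 1; after injection 0/45 × 46 = 0.
- SJC: baseline 1/44 × 44 = 1; after injection 0/43 × 44 = 0.
- One non-evaluable joint is far below the missing threshold, so the result is a valid 0. Nonresponder imputation is not triggered, and the patient counts as TJC = 0 or SJC = 0.

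**Several active joints, none improved, one injected**
- TJC: 3/46 × 46 = 3, then 2/45 × 46 = 2.04; change −0.96.
- SJC: 2/44 × 44 = 2, then 1/43 × 44 = 1.02; change −0.98.

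**Reach**
- The Schedule of Activities places Period 3 joint counts at Weeks 24, 36 and 52, plus any early termination visit. An injected joint can therefore affect at most three scheduled visits.
- If k of the n patients with a baseline count above 0 are injected in their only active joint, the proportion with a count of zero rises by at most k/n. It rises by less if some of them would have reached zero anyway. The documents give neither k nor n. Purely as an assumption, k/n of 2% to 5% gives a rise of at most 2 to 5 percentage points.

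**Check of the remedy**
- Keeping the single injected joint as active: 1/46 × 46 = 1 (SJC 1/44 × 44 = 1), so not zero.
- Change with the last score carried forward, TJC 3 example: 3/46 × 46 = 3; change 0.
- Change on the same 45 joints at both times: 2/45 × 46 = 2.04 before and after; change 0.

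**The case against.** The strongest reply is that the printed formula may not be the whole rule. Both joint-count entries point to Appendix 4, which is where handling of injected joints would sit. That stands as a limit: a special rule cannot be excluded, and its absence from the public text is not a gap in the plan. The point rests on the visible formula combined with the protocol's explicit exclusion. If Appendix 4 already deals with injected joints, the sponsor need only confirm it.

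A second reply is that no inference is at risk. This is correct. With injections barred in Period 2, the placebo-controlled joint-count tests are untouched unless there are protocol deviations. Joint counts lie outside the primary and major secondary endpoints, and Period 3 summaries carry no treatment comparison.

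Third, excluding the joint is defensible because it avoids crediting study drug with the steroid's local effect. That supports not scoring the joint as improved. It does not support counting the patient as TJC = 0, which is what removal from follow-up alone produces.

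Fourth, an injection is not necessarily a failure of ixekizumab. Patients from the adalimumab arm receive only placebo injections at Weeks 16 and 18 and start ixekizumab at Week 20. This also stands, and is why washout injections need separate reporting.

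Finally, injections can already be traced through the eCRF and the Period 3 concomitant-therapy summary. That helps a reader who looks for them but does not correct the joint-count tables.

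**Conclusion.** The point holds within limits. On the visible text, the descriptive Period 3 summaries can count a patient as TJC = 0 or SJC = 0 because the only active joint was injected. They can also show a fall in mean count, about 1 joint per injected joint in the examples, with no joint improved. The direction is known for a joint active at baseline. The size is not, because the documents give no injection rate.

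The documents do not support three stronger readings that a reader might infer:
- That the bias reaches the placebo-controlled results. The Period 2 ban on parenteral corticosteroids rules this out, deviations aside.
- That the plan labels these patients as having complete resolution of peripheral arthritis. The SAP uses that description only for enthesitis, and it keeps TJC = 0 and SJC = 0 as separate variables with separate baseline-positive populations.
- That percentage improvements in joint counts are inflated. Percent improvement is not a planned TJC or SJC output; only change and count of zero are.

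The conclusion assumes that Appendix 4 contains no different rule for injected joints.

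**What to change.** Amend SAP Table RHBV.6.4, reconciled with Appendix 4, for the Period 3 summaries:
- **TJC = 0 and SJC = 0:** after an injection, count the patient as not meeting the criterion if the injected joint was active at baseline or at its last pre-injection assessment. Including baseline matters because joint counts are weeks apart, so the last score alone can miss a flare between visits.
- **Change from baseline:** either carry forward the injected joint's last pre-injection score, or compute baseline and follow-up on the same set of joints.
- **Reporting:** give the number of patients injected by group, with injections during the adalimumab washout (Weeks 16 to 20) shown separately.
- **Unchanged:** keep the current exclusion for joints unevaluable at screening.

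The cost is SAP wording and a small derivation change. The injected joint is already identified in the eCRF, so neither data collection nor patient care changes. The downside is that a joint that truly settles is still counted as active, which is conservative. A joint quiet both at baseline and at its last assessment, but injected for a flare between visits, would still escape the zero-count rule and would appear only in the injection counts.

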#### **8.1.2.12.2. Swollen Joint Count**

The number of swollen joints will be determined by examination of 44 joints (22 joints on each side of the patient's body). The 44 joints to be assessed and classified as swollen or not swollen are detailed in site training materials. Any joints that require intra-articular injections during the study (according to Section 6.8) are to be excluded from evaluation from the time of the injection to the conclusion of the study.

Joint assessments must be assessed by a rheumatologist or health care provider who meets the qualifications for study assessments. To minimize interobserver variation, particularly during the Blinded Treatment Dosing Period (Period 2), it is recommended that the same assessor performs the SJC for a given patient. Missing, replaced, ankylosed, or arthrodesed joints will be identified by the investigator at the screening visit (Visit 1) and will be excluded from evaluation during the study.

The SJC data will be collected electronically.

#### **8.1.2.13. Nonsteroidal Anti-Inflammatory Drug Intake**

Information regarding NSAIDs intake will be collected in the eCRF and the ASAS-NSAID score will be calculated at baseline and through Week 52 (Dougados et al. 2011).

#### **8.1.2.14. Assessment of Spondyloarthritis International Society Health Index**

The ASAS HI is a disease-specific health-index instrument designed to assess the impact of interventions for SpA, including axSpA. This broader concept of health is included in the International Classification of Functioning, Disability, and Health, which has been published by the World Health Organization (WHO). The ASAS has applied this classification as a basis to define a core set of items relevant for patients with rad-axSpA. The 17-item instrument has scores ranging from 0 (good health) to 17 (poor health) (Kiltz et al. 2013). Each item consists of one question that the patient needs to respond to with either "I agree" (score of 1) or "I do not agree" (score of 0). A score of "1" is given where the item is affirmed, indicating adverse health. All item scores are summed to give a total score or index.

#### **8.1.2.15. Medical Outcomes Study 36-Item Short-Form Health Survey**

The SF-36 is a 36-item patient-administered measure designed to be a short, multipurpose assessment of health in the areas of physical functioning, role – physical, role – emotional, bodily pain, vitality, social functioning, mental health, and general health. The 2 overarching domains of mental well-being and physical well-being are captured by the mental component summary (MCS) and physical component summary (PCS) scores. The summary scores range from 0 to 100; higher scores indicate better levels of function and/or better health. Items are answered on Likert scales of varying lengths. The SF-36 version 2 (acute version) will be used, which utilizes a 1-week recall period (Ware 2000).

### **8.1.2.16. Fatigue Severity Numeric Rating Scale**

The Fatigue Severity NRS is a patient-administered, single-item, 11-point horizontal scale anchored at 0 and 10, with 0 representing “no fatigue” and 10 representing “as bad as you can imagine” (Naegeli et al. 2013). Patients rate their fatigue (**feeling tired or worn out**) by circling the one number that describes their worst level of fatigue during the previous 24 hours.

### **8.1.2.17. Work Productivity and Activity Impairment Questionnaire— Spondyloarthritis**

The WPAI-SpA consists of 6 questions to determine employment status, hours missed from work because of SpA, hours missed from work for other reasons, hours actually worked, the degree to which SpA affected work productivity while at work, and the degree to which SpA affected activities outside of work. The WPAI-SpA has been validated in the rad-axSpA patient population (Reilly et al. 2010). Four scores are derived: percentage of absenteeism, percentage of presenteeism (reduced productivity while at work), an overall work impairment score that combines absenteeism and presenteeism, and percentage of impairment in activities performed outside of work. Greater scores indicate greater impairment (Reilly Associates [WWW]).

### **8.1.2.18. Jenkins Sleep Evaluation Questionnaire**

The JSEQ is a 4-item scale designed to estimate sleep problems in clinical research. The JSEQ assesses the frequency of sleep disturbance in 4 categories: 1) trouble falling asleep, 2) waking up several times during the night, 3) having trouble staying asleep (including waking up far too early), and 4) waking up after the usual amount of sleep feeling tired and worn out. Patients report the number of days they experience each of these problems in the past month on a 6-point Likert scale ranging from 0 = “no days” to 5 = “22-30 days.” The total JSEQ score ranges from 0 to 20, with higher scores indicating greater sleep disturbance (Deodhar et al. 2010).

### **8.1.2.19. Laboratory Tests Used for Efficacy Measures and Disease Diagnosis**

#### **8.1.2.19.1. High Sensitivity C-Reactive Protein**

High sensitivity CRP will be the measure of acute phase reactant. It will be measured with a high sensitivity assay at the central laboratory to help assess the effect of ixekizumab on disease activity. The results will not be shared with the investigative sites after baseline randomization to maintain the study blind.

### **8.1.2.20. Imaging Used for Efficacy Measures and Disease Diagnosis**

#### **8.1.2.20.1. Imaging of Sacroiliac Joints and Spine**

For each patient, x-ray and MRI images will be collected according to the Schedule of Activities ([Appendix 2](#)), [Table RHBV.4](#), and will follow the study specific recommendations included in site training materials for the study. The SIJ x-ray will be used to confirm patients have radiographic sacroiliitis as defined by the mNY criteria. Magnetic resonance imaging of the SIJ and spine, collected at screening, Week 16, and Week 52 will generate objective data on the anti-inflammatory effect of the investigational drug. The screening x-ray of the spine will also serve as baseline for later evaluation of change from baseline in structural progression in the long-term study (RHBV).

The site will read the screening x-ray of the spine (cervical+lumbar) for presence or absence of total ankylosis to determine study eligibility. The site will then send the x-ray to the central reader to be maintained as a baseline for later structure assessments. All other images (x-ray of the SIJ and MRIs) are centrally read for eligibility and/or for assessment of treatment effect.

